### 3. SUMMARY OF PROTOCOL CHANGES

2367

2368

2369 **v2.1** – Original trial protocol. v1.0 of the protocol was a draft protocol that was updated following the  
2370 initial investigator meeting.

2371 **v2.2** – Added external study sites. Modifications to protocol at coordinating center (reflected in v2.3  
2372 for all sites).

2373 **v2.3** – Change in exclusion criteria from CKD  $\geq 3b$  [GFR < 45ml/hr] to receiving renal replacement  
2374 therapy. Clarification that sepsis should be the likely cause of hypotension resulting in vasopressor  
2375 requirement and that consent/enrollment should be within 24-hours of meeting inclusion criteria.

2376 Change in contingency should open label thiamine be prescribed by the clinical team. Allowance for  
2377 a consideration of sample size adjustment should the SOFA score and/or mortality for the full study  
2378 cohort (examined without consideration of study group) fall below that anticipated in the power  
2379 analysis. Clarification of adverse event reporting procedures.

2380 **v2.4** – Addition of study site. Correction of oversight in exclusion criteria with respect to clinical  
2381 ascorbic acid supplementation. Clarification of SOFA scale to assign a renal SOFA score of 4 if a  
2382 patient is started on renal replacement therapy.

2383

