#### **3.3 Exclusion criteria**

Exclusion criteria:

- 1) Member of a protected population (pregnant, prisoner)
- 2) Known history of kidney stones within the past 1 year (not including incidentally noted stones noted on imaging studies)
- 3) End stage renal disease requiring dialysis (hemodialysis or peritoneal dialysis)
- 4) Known history of G6PD deficiency
- 5) Known history of Hemochromatosis
- 6) Comfort Measures Only status
- 7) Anticipated death within 24-hours despite maximal therapy (as determined by the enrolling physician)
- 8) Receiving supplemental vitamin B1 in a dose greater than that contained in a multivitamin (<2mg)
- 9) Clinical indication for steroids (e.g. chronic use) as determined by the clinical team providing this drug
- 10) Clinical indication for ascorbic acid supplementation in any form
- 11) Clinical indication for vitamin B1 as determined by the clinical team providing this drug
- 12) Known allergy to vitamin C, hydrocortisone, or vitamin B1

Justification of Inclusion and Exclusion Criteria: The inclusion criteria were chosen to isolate a septic participant population with high risk of organ injury and death. The exclusion criteria were chosen to minimize the risk of potential harm and to ensure that participants enrolled do not already have chronic end-stage renal failure with a high likelihood of early need for renal replacement therapy. By evaluating this high-risk population (i.e., most likely to die), we will target those most likely to benefit and therefore increase the probability of showing efficacy.

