##### *4.5.2 Specimen samples*

At the T1, T2, T3, and T4 time points, blood will be sent for complete blood count (including hemoglobin, white blood cell count, platelet count), a serum chemistry (including sodium, potassium, chloride, bicarbonate, blood urea nitrogen, creatinine, glucose, aspartate transaminase, alanine transaminase, and total bilirubin), and a venous blood gas to measure lactate. These tests will be performed by the clinical laboratory at each site. As many of these laboratory tests are commonly obtained for clinical purposes, these tests do not need to be repeated if a result is available from the clinical care of the participant within 2 hours of the time point (or within 12 hours of the T4 time-point).

In addition to traditional clinical markers, blood will be obtained for future biomarker analysis (including inflammatory biomarkers, markers of endothelial function, and markers of mitochondrial function), and measurement of vitamin C, vitamin B1, and cortisol levels. The total volume of blood that may be drawn for a participant at each time point will not exceed 60mls. Levels of vitamin C, vitamin B1, and cortisol will be measured at time T1 and time T3 only. 20ml of urine will be collected for future biomarker analysis at T1, T2, and T3.

[figure not shown]
If performed as part of standard-of-care, results of urinalysis and urine sediment testing will be collected prior to enrollment.

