##### 5.1.2 Key Secondary Outcomes

Incidence of Acute Renal Failure – Renal failure will be defined as the development of Kidney Disease Improving Global Outcomes [KDIGO] Stage 3 acute kidney injury during the index ICU stay after study enrollment.

KDIGO Stage	Serum creatinine criteria	Urine output criteria
1	Increase in serum creatinine of more than or equal to 0.3 mg/dl ( $\geq$ 26.4 $\mu$ mol/l) or increase to more than or equal to 150% to 200% (1.5- to 2-fold) from baseline	Less than 0.5 ml/kg per hour for more than 6 hours
2	Increase in serum creatinine to more than 200% to 300% (> 2- to 3-fold) from baseline	Less than 0.5 ml/kg per hour for more than 12 hours
3	Increase in serum creatinine to more than 300% (> 3-fold) from baseline (or serum creatinine of more than or equal to 4.0 mg/dl [<math>\geq</math> 354 <math>\mu</math>mol/l]) with an acute increase of at least 0.5 mg/dl [44 <math>\mu</math>mol/l])	Less than 0.3 ml/kg per hour for 24 hours or anuria for 12 hours OR New renal replacement therapy (RRT)

**30-Day Mortality** – Mortality at 30-days. This will be assessed by review of the medical records if the participant remains in the hospital or if the participant expired while in the hospital. If the participant was discharged, 30-day mortality will be assessed by contacting the participant by phone or by searching the National Center for Health Statistics (NCHS) National Death Index (NDI) consistent with a recent multicenter phase III trial in sepsis. Phone calls will be made by the research team at each site.

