## 6. SAMPLE SIZE CALCULATION AND STATISTICAL ANALYSIS PLAN

### 6.1 Sample size calculation

The study has been powered to have at least 80% power for the primary outcome and all key secondary outcomes as follows:

**SOFA Score:** Based on preliminary data, we conservatively anticipate a decrease in SOFA score of 6 (standard deviation [SD]: 4) in the treatment group and 4 (SD: 2) in the placebo group. With these estimates, enrollment of **200 participants (100/arm)** at an alpha of 0.05 and using a t-test with unequal variance, the trial will provide > 99% power to detect a statistical significant difference between groups.

**Kidney Injury:** Based on preliminary data from our study of vitamin B1 in septic shock, we anticipate that 30% of participants in the treatment group and 55% in the placebo group will have renal failure which will result in a 94% power for this outcome. This calculation and following calculation were performed using the Fisher's exact test.

**Mortality:** Based on preliminary data, we anticipate that the control group will have a mortality of 40%. We estimate a treatment effect of 50% (risk ratio: 0.50) resulting in a mortality of 20% in the treatment group. With these estimates, 182 participants will lead to 80% power. To further increase

the trial's power and due to potential loss-to-follow-up, we will aim to enroll 200 participants. These estimates are conservative compared to the Marik et al. study which found a treatment effect corresponding to a risk ratio of 0.21 which persisted in adjusted analysis.

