## 6.2 Statistical analysis plan

### 6.2.1 General considerations

The statistical analyses and reporting will adhere to the CONSORT guidelines. All tests will be two-sided, a p-value  $< 0.05$  will be considered significant, and all confidence intervals will have 95% coverage. All analyses will be conducted on a modified intention-to-treat basis only including participants receiving at least the first dose of the study medications. In a double-blind trial, this approach is unbiased while increasing precision. The two groups will be compared in relation to baseline characteristics using descriptive statistics.

The persons conducting the statistical analysis will be blinded to the randomized allocation. Groups will be designated as "A" and "B" until all pre-specified analyses are performed and shared with all authors and the Data Safety Monitoring Board.

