### 6.2.2 SOFA score and renal failure

The change in SOFA score will be calculated and compared between groups using the Wilcoxon Rank Sum test (if the change is not normally distributed) or by a t-test if the change is approximately normally distributed. Fisher's exact tests will be used to compare the incidence of renal failure during the index ICU stay.

If a participant expires prior to the 72-hour time point, SOFA scores will be imputed based on a pre-defined plan as follows. If a participant expires before 24-hours has elapsed, a 20% increase from baseline will be imputed. If a participant expires between 24-hours and 48-hours, a 15% increase from the 24-hour time point will be imputed. If a participant dies between 48-hours and 72-hours, a 20% increase from the 24-hour time point will be imputed. Sensitivity analyses will be performed using various other imputation techniques. Specifically, we will perform 1) a sensitivity analysis in which the worst possible SOFA score (score of 24) is imputed for those participants who expire, 2) a sensitivity analysis in which the last SOFA score for participants who expire will be carried forward, and 3) a sensitivity analysis in which only those patients who survive to 72-hours are included. These sensitivity analyses were chosen to model 'worst-possible' and 'best-possible' scenarios. For the secondary outcome of renal failure, participants who expire during their ICU stay will be assessed to have developed renal failure if they demonstrated any degree of unresolved KDIGO acute kidney injury prior to death. If there was no evidence of acute kidney injury prior to death or if kidney injury had fully resolved, these participants will be assessed as not having developed renal failure.

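### Renal failure is compared by an unadjusted Fisher test although creatinine is available at T1; pre-specifying adjustment for it is a free improvement of uncertain, possibly small, size

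*SAP*

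**What the plan says.** Protocol 6.2.2, repeated in the SAP, plans the renal comparison in one sentence: Fisher's "exact tests will be used to compare the incidence of renal failure during the index ICU stay". No covariate or stratum enters, and 6.2.1 uses baseline variables only to describe the arms. The same section sets the level: "All tests will be two-sided, a p-value" below 0.05 counts as significant.

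Section 6.1 gives the planning rates: "we anticipate that 30% of participants in the treatment group and 55% in the placebo group will have renal failure". For Fisher's test with 100 participants per arm, it then states the resulting figure ("which will result in a 94% power for this outcome").

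The outcome (5.1.2) is KDIGO Stage 3 injury arising in the index ICU stay after enrollment. It can be met by a more than 3-fold creatinine rise from baseline ("or serum creatinine of more than or equal to 4.0 mg/dl" with an acute rise of at least 0.5), by low urine output, or by new renal replacement therapy. Under 6.2.2, a death in the ICU with any unresolved kidney injury also counts.

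Creatinine is part of the T1 panel in 4.5.2 ("a serum chemistry (including sodium, potassium, chloride, bicarbonate, blood urea nitrogen, creatinine, glucose" and others). T1 is timed at 0 hours, before study drug. A clinical result within 2 hours may stand in for it.

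Section 3.3 now excludes only "End stage renal disease requiring dialysis (hemodialysis or peritoneal dialysis"). The pre-v2.3 protocol reprinted in the SAP file excluded known CKD stage 3b or worse, and the SAP's summary of changes logs the move under v2.3 ("GFR < 45ml/hr] to receiving renal replacement"). That earlier protocol has the same Fisher test and the same 30%, 55% and 94%.

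**The concern.** A pre-treatment measurement that probably predicts the outcome is already collected and then left out of the comparison. With a binary outcome, adjusting for a prognostic baseline variable gives a more powerful test of treatment and removes the effect of any chance imbalance in that variable.

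Section 5.2 says a renal benefit could change practice independently of other factors. The planning rates come from an earlier study of vitamin B1 alone. If the true effect is smaller than 25 percentage points, power falls quickly. The Sample Size Adjustment text lets a low renal event rate prompt a review, but its specific power targets name only SOFA and mortality, so no stated target protects renal power.

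**Working it through.** **1. The plan's own figure.** Inputs from 6.1 and 6.2.1: 100 per arm, 30% v 55%, two-sided 0.05, Fisher's test. Power is the sum, over all pairs of event counts, of the product of the two binomial probabilities wherever the Fisher p-value is at most 0.05. Result: 93.9%, against the stated 94%. The same sum at 40% v 55% gives 53.0%.

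**2. Why T1 creatinine is likely prognostic.** Assume that T1 is the KDIGO baseline b; the documents do not say so. The creatinine routes then require min(3b, max(4.0, b + 0.5)) mg/dl:

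| b (mg/dl) | Stage 3 threshold | Rise needed |
|---|---|---|
| 1.0 | 3.0 | 200% |
| 2.0 | 4.0 | 100% |
| 3.0 | 4.0 | 33% |
| 3.5 | 4.0 | 14% |

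The proportional rise needed is flat at 200% up to 4.0/3 = 1.33 mg/dl and then falls. The absolute rise needed peaks near 1.33. The relation may therefore not be linear.

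**3. What adjustment could add.** Simulation, 20,000 trials per setting, 100 per arm, marginal rates held fixed, standardised log T1 creatinine linear on the logit scale. Its strength (AUC) is assumed. The unadjusted likelihood-ratio (LR) test separates the covariate's contribution from that of leaving Fisher's conservative test. It does not depend on the AUC, so one value is used per scenario: 95.5% and 58.6% (simulated values ran from 95.4% to 95.6% and from 58.2% to 58.8%).

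| AUC | 30% v 55%: adjusted | minus 95.5 | 40% v 55%: adjusted | minus 58.6 |
|---|---|---|---|---|
| 0.61 | 95.9% | 0.4 | 58.1% | -0.5 |
| 0.70 | 97.1% | 1.6 | 62.5% | 3.9 |
| 0.77 | 98.3% | 2.8 | 67.8% | 9.2 |
| 0.82 | 99.2% | 3.7 | 73.0% | 14.4 |

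The simulation standard error near 58% is about sqrt(0.586 × 0.414 / 20,000) = 0.35 points, so the -0.5 means no detectable gain. Leaving Fisher's test is worth 95.5 - 93.9 = 1.6 points at the planned rates and 58.6 - 53.0 = 5.6 points at 40% v 55%. That is a separate matter and is not counted here.

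With no treatment effect (55% in both arms), rejection rates were 3.8% to 4.0% for Fisher, 5.3% to 5.5% for the unadjusted LR test and 5.1% for the adjusted test.

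**4. What AUC is plausible.** Take T1 creatinine as lognormal (median 1.6 mg/dl, log-SD 0.6; assumed), apply the rule in step 2, fix the event rate at 55%, and vary the log-SD of the rise from 0.5 to 0.8.

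- If the fold-rise is independent of T1 and 0 to 50% of participants reach the endpoint by a route unrelated to T1, the AUC is 0.54 to 0.76.
- If the absolute rise is independent of T1, with 0 to 40% by other routes, it is 0.57 to 0.61.

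The upper rows of the table in step 3 are therefore the safer guide.

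**5. Whether v2.3 matters.** Let 0 to 30% of participants be newly admitted with CKD, shifted up by 1.5 SD (assumed), so that the creatinine SD goes from 1.00 to 1.21. Fisher's power stays at about 94% (planned rates) and 53% (40% v 55%). Adjusted power moves from 97.2% to 97.7%, and from 62.9% to 64.7%.

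**The case against.** The strongest reply is that nothing here is wrong. Fisher's test is valid and conservative, and at the planned rates its 94% is well above the trial's 80% goal. Chance imbalance is already covered by the type I error, and baseline characteristics will be reported by arm. All of that stands. Adjustment is a gain in efficiency and does not correct an invalid test.

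A second reply is that the endpoint may depend on T1 creatinine less than expected. Urine output, new renal replacement and death with unresolved injury all produce events, and the KDIGO baseline may be a pre-illness value, in which case the percentages in step 2 do not apply. This also stands, and it is why the gain may be near zero.

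A reader might infer more: that v2.3 widened the spread of creatinine and thereby cost the renal comparison power. The documents do not support that. Fisher's power is fixed by the two event rates, and the same unadjusted test stood before the amendment. The earlier exclusion covered known CKD and set no limit on T1 creatinine, so high values from acute injury were always eligible. No figure is given for the spread or for the share newly admitted. The change log entry is not itself an error.

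**Conclusion.** The point holds as a free improvement to 6.2.2. The planned test is sound and its stated power is right. Adjusting for T1 creatinine would probably add some power, but how much rests on an assumed AUC of about 0.6 to 0.8. The covariate's own contribution is roughly 0 to 4 points at 30% v 55%, where little can be gained, and roughly 0 to 14 points at 40% v 55%, a scenario outside the plan that shows what happens if the effect is smaller. Both ranges also assume a linear effect of log creatinine on the logit scale, and the non-creatinine routes to the endpoint may hold the gain at the low end. Amendment v2.3 is background and changes neither the validity nor the power of the planned test.

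**What to change.** In 6.2.2, pre-specify a logistic regression of renal failure on treatment and log T1 creatinine. Report a standardised risk difference and risk ratio with 95% confidence intervals. A Mantel-Haenszel comparison stratified by T1 creatinine (for example below 1.2, 1.2 to 1.9, and 2.0 mg/dl or more, following the SOFA bands) would also serve and does not assume linearity. Choose one in advance and keep Fisher's test as the unadjusted check. It would help to state in 5.1.2 which creatinine is the KDIGO baseline, and in 6.2.2 which result is used when a clinical value stands in for T1.

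The cost is a sentence or two of text and a few lines of code. No extra participants, visits or samples are needed.
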